11.3. Eliciting Adverse Event Information

The investigator is to report all directly observed AEs and all AEs spontaneously reported by the patient. Patients will be questioned daily about AEs if they are able to respond, and then followed through the duration of the study.

[figure not shown]
11.4. Reporting

Each AE is to be classified by the investigator as serious or non-serious.

All AEs that occur in study subjects during the AE reporting period specified in the protocol must be reported, whether or not the event is considered to be related to study drug.

11.4.1. Reporting Period

The AE reporting period for this study begins upon initiation of study drug and ends up to 16 days after randomization (14 days of drug dosage plus two days), while SAEs will be continued to be reported up to Day 28, and will be assessed via follow-up, or through the patient's chart. However, AEs considered secondary to protocol mandated procedures should be reported post signing of the informed consent form (ICF), whether or not they occur before or after initiation of study drug. Subjects discharged from the hospital will be contacted on day 7, 14, and 28 to assess for SAEs. In addition, SAEs that occur during the protocol-defined AE reporting period that the investigator assesses as unexplained and related to the study drug will also be reported as an SAE to the UTHealth IRB and the FDA. AEs and SAEs that occur after the protocol-defined period that the

investigator assesses as related to the study drug will also be reported as an AE to UTHealth. If the event is serious, related, and unexpected, the event will be reported to the investigator IRB and the FDA.

11.4.2. Reporting AEs

All AEs (serious and non-serious) are to be reported on the AE CRF in the clinical database during the AE reporting period as described in Section 11.1.

11.4.3. Reporting SAEs

Any SAE, regardless of causal relationship, will be reported to the sponsor's designee within 24 hours after the investigator becomes aware of the SAE. Compliance with this time requirement is essential so that the sponsor may comply with its regulatory obligations. Additionally, it may be necessary for UTHealth (or designee) to directly communicate with the investigator if additional information is required.

The initial SAE report should be completed as fully as possible but will contain, at a minimum item number 1 to 6:

- 1. Subject number/ID, sex, and age
- 2. The date of report
- 3. Name of the reporter
- 4. Name of the suspected medicinal product
- 5. A description of the event, including event term(s), seriousness criteria, and a clinical summary of the event
- 6. Causality assessment

The investigator will assess the relationship to each specific component of the study treatment. A SAE Report Form will be sent to the sponsor or its designee via email or the investigator will call the sponsor or its designee SAE hotline within 24 hours of being made aware of the SAE.

Refer to the SAE Report Form and SAE Report Form Guidelines for more details on SAE reporting, including timelines, and email for reporting and the contact information for any questions regarding SAE reporting.

The investigator must report follow-up information relating to an SAE to the study safety monitor as it becomes available by submitting a REDCAP SAE Report Form. The subject will be observed and monitored carefully until the condition is resolved or stabilizes.

All deaths are to be thoroughly investigated and reported to the UTHealth IRB. Autopsy reports and death certificates are to be obtained, if possible. In-hospital deaths will be investigated via electronic medical records (EMR). Out-of-hospital deaths will be investigated by calling their family, and reviewing available death certificates.

In addition to the sponsor's responsibility for reporting SAEs to all applicable regulatory agencies, Institutional Review Board (IRB) or Independent Ethics Committee (IEC), and investigators within the required timeline, UTHealth and/or its designee are responsible for reporting SAEs to all applicable regulatory agencies, central ethics committees, and investigators as well within the required timeline.

11.5. Relationship to Study Drug

The investigator must provide an assessment of causality (relationship to study drugs) at the time of the report. If causality is difficult to determine, for example, due to incomplete clinical information at the time of the report, the investigator must use clinical judgment under consideration of the criteria outlined below and provide a causality assessment. It is also good practice to include a rationale for the causality assessment.

The assessment of causal relationship to study drug will be evidence-based, and not based on the premise that all AEs are possibly causally related to study drug until proven otherwise.

Examples of evidence that would suggest a causal relationship between the study drug and the AE include the occurrence of an AE that is uncommon and known to be strongly associated with drug exposure (e.g., angioedema, hepatic injury, Stevens-Johnson Syndrome), or an AE that is uncommon in the population exposed to the drug.

Algorith	m to Determine Relatedness of Adverse Event in Study Agent					
Unrelated	The temporal relationship between treatment exposure and the adverse even is					
	unreasonable or incompatible and/or adverse event is clearly due to extraneous causes					
	(e.g. underlying disease, environment).					
Unlikely	Must have both of the following two (2) conditions, but may have reasonable or only					
	tenuous temporal relationship to intervention:					
	1. Could readily have been produced by the subject's clinical state, environmental, or other interventions.					
	2. Does not follow known pattern of response to intervention.					
Reasonable Possibility	Must have at least two (2) of the following three (3) conditions:					
	1. Has a reasonable temporal relationship to intervention					
	 Could not have readily been produced by the subject's clinical state or environmental or other interventions 					
	3. Follows a known pattern of response to intervention.					
Definitely	Must have all three (3) of the following conditions:					
	1. Has a reasonable temporal relationship to intervention					
	2. Could not possibly have been produced by the subject's clinical state or					
	have been due to environmental or other interventions					
	3. Follows knows pattern of response to intervention.					

The site investigator, on the basis of his or her clinical judgment and the following definitions, determines the relationship of the AE to the protocol intervention as one of the following:

Default assessments using the 'related' category without supportive evidence for a causal relationship to study drug is generally uninformative and does not contribute meaningfully to the development of the safety profile of the drug or to subject protection.

Investigators are encouraged to choose the most plausible cause for the event(s) from the following list: medical history, lack of efficacy/worsening of treated condition, study treatment, other treatment (concomitant, or previous), withdrawal of study treatment, administration error, protocol-related procedure, others (specify).

11.6. Severity

The investigator will assess each AE using the CTCAE guidelines to describe the maximum severity of the AE:

- **Grade 1 Mild** asymptomatic or mild symptoms; clinical or diagnostic observations only; intervention not indicated.
- **Grade 2 Moderate** minimal, local or noninvasive intervention indicated; limiting age appropriate instrumental ADL.
- Grade 3 Severe or medically significant but not immediately life threatening hospitalization or prolongation of hospitalization indicated; disabling; limiting self care ADL.
- Grade 4 Life threatening consequences urgent intervention indicated.
- Grade 5 Death related to AE.

Note that a severe AE is not necessarily a serious AE. For example, a headache may be severe in intensity, but would not be classified as serious unless it met one of the criteria for serious events listed above, see Section 11.4.3.

11.7. Emergency Unblinding:

A representative of the study leadership will always be available using 24-hour telephone number for communication with investigators and healthcare providers caring for the patient.

[figure not shown]
If a clinician requests emergency unblinding of study drug in response to a clinical event, the study representative will discuss the clinical utility of unblinding with the clinician. Emergency unblinding will only occur if the clinical and investigator agree that it is necessary to treat the patient. Emergency unblinding should be rare as there is no antidote to the drug, and it is given orally. All requests for emergency unblinding will be reported to the study safety officer. The safety officer will then determine if the patient should continue to receive study medication.

11.7.1 Non-Emergency Un-blinding

At times the sponsor or designee may request un-blinding of safety events in accordance with their reporting responsibilities. In these cases, if the treatment team does not need to be un-blinded, the database manager will un-blind the sponsor or their designee but will not un-blind the clinical or research team.

11.8 Follow-up of Unresolved Events

All AEs will be followed until they are resolved, or the investigator assesses them as chronic or stable or the subject's participation in the study ends (i.e., until a final report is completed for that

subject).

All SAEs and non-serious events that are ongoing at the time a subject's participation in the study ends and that are assessed by the investigator as related to the study drug, will continue to be followed until they resolve or until the investigator assesses them as "chronic" or "stable". Followup information will be reported to UTHealth on the appropriate CRF or paper SAE Report Form if EDC is unavailable.

More details of the study safety plan are described in the study Manual of Procedures.

12. Sample Size and Power Calculation

The trial will investigate the superiority of vadadustat 900 mg per day to placebo for the prevention and treatment of ARDS among COVID-19 patients, defined by the proportion of patients at day 14 who are dead (8) or hospitalized, on invasive mechanical ventilation or ECMO (7) or hospitalized, on noninvasive ventilation or high flow oxygen devices (6) on the NIAID-OS (i.e. decrease in the proportion of participants with NIAID-OS ≤ 6 at day 14).

Anticipated sample size for the current study is N = 650. An evaluation by the DSMB will occur following ascertainment of 14-day safety outcomes for the first 30 patients that are randomized and dosed, and a second at the first 120 (i.e. n = 60 receiving Vadadustat).

[figure not shown]
Bayesian analysis for superiority will occur following ascertainment of outcome at fourteen days after randomization of N = 650 patients. We stipulate that a posterior probability of a > 2.5% decrease in the proportion of NIAID-OS \geq 6 as a function of treatment that is > 0.85 constitutes sufficient evidence to declare that the active treatment condition is superior to placebo. The prior distribution for analysis will be ~Beta(a= 1, b = 1), or in the presence of covarying for stratification factors ~Normal (µ=0, σ 2=1 x 10) for the coefficients in the log-form of the appropriate generalized linear model.

We anticipate a decrease in the proportion of NIAID-OS \geq 6 participants due to treatment will be approximately 15%, with preliminary data suggesting a rate of 25.1% in the placebo condition. Assuming this effect, K = 1000 Monte Carlo clinical trial simulations, for N = 650 participants and the previously stated decision rules resulted in detection of a > 2.5% decrease in NIAID-OS \geq 6 due to the active treatment 99.1% of the time with a Type I Error rate of 3.5%. For more modest effects, 12.5% and 10% decreases in NIAID-OS \geq 6, the current sample and decision rules will lead to detection 96.1% and 86.3% of the time with Type I Error rates of 4.8% and 3.7% respectively.

13. Statistical Analysis

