estimate the probability of observing the data (or data more extreme) given that the null hypothesis is true; Bayesian analyses estimate the probability of the alternative hypothesis given the observed data (Wijeysundera et al 2009). Bayesian probability estimates incorporate prior information about plausible parameter values (i.e., the prior distribution) and the observed data (i.e., the likelihood). Combining these two distributions forms the posterior distribution which permits evaluation of the probability that the true value of the parameter falls in some range.

[figure not shown]
3. Primary Objectives

To assess the efficacy and safety of vadadustat for the prevention and treatment of ARDS in hospitalized patients with COVID-19

4. Study Design

This is a phase 2 multicenter, randomized, double-blind, placebo-controlled Bayesian clinical trial of vadadustat for the prevention and treatment of ARDS in hospitalized patients with COVID-19. Extended follow-up of participants will occur at 6, 12, and 24 months (see section 8.4.1).

Following screening, patients will be randomized in a 1:1 ratio to either vadadustat 900 mg or placebo. Randomization will be stratified by site, and MSOFA score at baseline (<4 and ≥4)

5. Study Outcomes:

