13.1. Specific Statistical Hypothesis Primary Outcome

Among adult hospital admissions with lab-confirmed diagnosis of COVID-19, vadadustat 900 mg will demonstrate superiority to placebo as defined by a lower probability, at treatment day 14, of

death (8) or hospitalization, on invasive mechanical ventilation or ECMO (7) or hospitalization, on non-invasive ventilation or high flow oxygen devices (6) on the NIAID-OS. Generalized linear modeling will evaluate the probability of patients demonstrating this status at day fourteen of treatment as a function of treatment condition after covarying for stratification variables.

Secondary Outcome

Among adult hospital admissions with lab-confirmed diagnosis of COVID-19, vadadustat 900 mg will demonstrate superiority to placebo as defined by a higher probability, at treatment day 14, of recovery on the MSOFA scale (MSOFA = 0). Generalized linear modeling will evaluate the probability of patients demonstrating an MSOFA = 0 at day fourteen of treatment as a function of treatment condition after covarying for stratification variables.

[figure not shown]

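### Section 12's printed powers (99.1 / 96.1 / 86.3%) do not follow from its stated inputs, which give about 99.9 / 98.8 / 91.4%

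*Combined protocol and SAP*

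**What the plan says.** Section 12 fixes the sample size ("Anticipated sample size for the current study is N = 650") and the success rule: superiority is declared if the posterior probability of a decrease of more than 2.5% in the proportion with NIAID-OS 6 or worse at day 14 is above 0.85. Efficacy is analysed once, when all 650 patients have their day-14 outcome. Section 4 states that "patients will be randomized in a 1:1 ratio to either vadadustat 900 mg or placebo".

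The prior is Beta(1,1) for the proportions, "or in the presence of covarying for stratification factors", Normal with mean 0 and variance 10 on the model coefficients. Section 13.1 plans to model the primary outcome "as a function of treatment condition after covarying for stratification variables".

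The assumed effect is a decrease of about 15%, "with preliminary data suggesting a rate of 25.1% in the placebo condition". From 1000 simulated trials, Section 12 reports detection "due to the active treatment 99.1% of the time with a Type I Error rate of 3.5" per cent. For decreases of 12.5% and 10% the same design "will lead to detection 96.1% and 86.3% of the time with Type I Error rates of 4.8% and 3.7% respectively". It does not say which of the two models was simulated, and it states no missing-outcome rate.

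**The concern.** With two arms of 325, a fixed placebo rate, flat priors and one analysis, the power of this rule can be computed without simulation. The printed powers should therefore match an exact calculation to within the noise of 1000 replicates. Two of the three are visibly too low.

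These are the only operating characteristics given for a non-standard rule (a 2.5-point margin and a 0.85 threshold), and they are the evidence that the rule behaves as claimed at this sample size. If they come from a different placebo rate, sample size or model, the simulation and the written assumptions describe different trials, and the 25.1% in the text is not shown to be the basis of the justification.

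**Working it through.** **Inputs.** 325 per arm (650 at 1:1; Sections 12 and 4); placebo rate 0.251; active rate 0.251 − d with d = 0.15, 0.125, 0.10; Beta(1,1) priors; success if Pr(decrease > 0.025 | data) > 0.85; 1000 replicates (all Section 12). The effects are read as absolute percentage points. Read as relative decreases, the powers would be only about 25 / 20 / 15%, so that reading is excluded.

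**1. Normal approximation, which can be checked by hand.** Under flat priors the rule succeeds when the observed difference exceeds 0.025 by about z(0.85) = 1.036 standard errors, so

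power ≈ Φ[(d − 0.025)/SE − 1.036], where SE = √{[0.251 × 0.749 + p(1 − p)]/325} and p = 0.251 − d.

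- d = 0.15, p = 0.101: SE = √[(0.1880 + 0.0908)/325] = 0.02929; 0.125/0.02929 − 1.036 = 3.231; power 99.94%.
- d = 0.125, p = 0.126: SE = √[(0.1880 + 0.1101)/325] = 0.03029; 0.100/0.03029 − 1.036 = 2.265; power 98.8%.
- d = 0.10, p = 0.151: SE = √[(0.1880 + 0.1282)/325] = 0.03119; 0.075/0.03119 − 1.036 = 1.368; power 91.4%.
- d = 0 (null): SE = 0.03401; −0.025/0.03401 − 1.036 = −1.771; Type I error 3.8%.

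**2. Exact calculation.** Each pair of event counts was enumerated and weighted by its binomial probability. The rule was applied to numerically integrated Beta posteriors.

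| Decrease | Printed | Exact | Gap (points) | SE of printed value | Gap in SE |
|---|---|---|---|---|---|
| 15 points | 99.1% | 99.94% | 0.8 | √(0.991 × 0.009/1000) = 0.0030 | 2.8 |
| 12.5 points | 96.1% | 98.81% | 2.7 | √(0.961 × 0.039/1000) = 0.0061 | 4.4 |
| 10 points | 86.3% | 91.40% | 5.1 | √(0.863 × 0.137/1000) = 0.0109 | 4.7 |

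The exact Type I error is 3.83%. A 20,000-trial Beta-sampling simulation agreed (99.95 / 98.88 / 91.42%, Type I 3.80%). If the exact powers are right, the chance of a 1000-replicate run at or below the printed figure is about 3 × 10⁻¹⁰ for 96.1% and 6 × 10⁻⁸ for 86.3%.

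**3. Type I error.** The null does not depend on the assumed effect, so 3.5, 4.8 and 3.7% estimate one quantity. Their mean is (3.5 + 4.8 + 3.7)/3 = 4.0%. With 3000 replicates the SE is √(0.04 × 0.96/3000) = 0.36 points, so 4.0% is about 0.5 SE from 3.83%. These figures are consistent with the stated rule.

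**4. Could an unstated detail explain the powers?**

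- *Covariate adjustment.* A logistic model with Normal(0, variance 10) priors and a marginal risk difference was simulated 4000 times. Assumptions not in the documents: MSOFA of 4 or more in 30–50% of patients, odds ratio 2–4, and 4–8 sites. Power was at least 99.98%, then 99.0–99.4% and 92.0–93.6%. This is further from print.
- *Missing outcomes.* Complete-case power is 99.9 / 98.2 / 89.2% with 10% missing, 99.7 / 97.2 / 86.5% with 20%, and 99.5 / 96.2 / 84.2% with 28%. Section 12 states no such rate. The 10% attrition in Section 18.8.2 belongs to the long-term follow-up and would not close the gap.
- *Other readings at N = 650 and 25.1%.* A threshold of 0.90 gives 99.9 / 97.8 / 86.8% but Type I error of 2.1%. A zero margin gives 100 / 99.9 / 98.5% with Type I error of 15%. Allocation of 2:1 gives 99.9 / 98.2 / 88.9%. None matches both the powers and the error rates.

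**5. What does fit the three printed powers** (chi-square on 3 df; the stated inputs score 215):

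- placebo rate set to 25.1% plus the effect: 99.2 / 95.7 / 85.1% (1.6)
- fixed placebo rate of 35%: 99.5 / 96.3 / 85.1% (4.2)
- fixed placebo rate of 36%: 99.4 / 96.0 / 84.8% (3.5)
- fixed placebo rate of 38%: 99.3 / 95.6 / 84.3% (3.9)
- N = 470 at 25.1%: 99.5 / 96.2 / 84.2% (7.3)

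Several explanations fit, so the cause cannot be identified from the documents.

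**The case against.** The strongest reply accepts the arithmetic and disputes what follows from it. Section 12 does not name the simulated model, so the finding may be incomplete reporting rather than a wrong number. Section 13.2 plans multilevel models with clustering by site, which the adjusted check above did not simulate. If the treatment effect is assumed to vary between four sites with a standard deviation of 5 points, a pooled analysis at 25.1% and N = 650 gives 99.1 / 95.5 / 85.3%, which fits print as well as the best placebo-rate explanation. The headline 15-point power is off by only 0.8 points, the discrepancy is conservative, and no design element changes.

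Part of this stands. The placebo rate is not proven to be the cause, and the idea that the effect was added to 25.1% instead of subtracted remains conjecture. The 8.6% risk of missing a 10-point effect belongs to the unadjusted, complete-data model; the adjusted runs imply 6.4–8.0%. The 0.8-point gap is immaterial in size.

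The rest does not rescue the figures. The documents state no site variation in the treatment effect. If it is also put into the null, Type I error rises to about 7.6–7.7%, which the printed 3.5–4.8% does not fit. A reader using what Section 12 states still cannot recover 96.1% or 86.3%.

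**Conclusion.** The concern holds. At the stated inputs the rule has power of about 99.9 / 98.8 / 91.4%, not 99.1 / 96.1 / 86.3%. The material discrepancies are the 2.7 and 5.1 points for the two smaller effects. For a 10-point effect the risk of missing it is 8.6%, against the 13.7% implied by print. This rests on absolute-point effects, 325 evaluable patients per arm and the unadjusted Beta(1,1) analysis.

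The printed Type I errors are not wrong, and N = 650 is not called into question, because the stated inputs deliver more power than is claimed. What fails is the link between the stated assumptions and the reported simulation. It should be repaired before the operating characteristics are relied on.

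**What to change.** - Check the simulation code for the placebo rate, sample size, model and direction of the effect that it used.
- Re-run it with placebo at 25.1% and active at 25.1% minus the effect, under the covariate-adjusted model of Section 13.1, with more replicates (for example 20,000). As a check, the unadjusted Beta(1,1) version should return about 99.9 / 98.8 / 91.4%.
- In Section 12, state the model, the assumed strata and the missing-outcome rate, and restate the powers from that run. Alternatively, disclose and justify the inputs actually used, such as a higher placebo rate.
- Report one Type I error, and state that the effects and the 2.5% margin are absolute percentage points.
- Editorial: the parenthesis "i.e. decrease in the proportion of participants with NIAID-OS ≤ 6 at day 14" has the inequality reversed. The same sentence and the decision rule imply 6 or higher.

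The cost is one simulation re-run and a few sentences. Design, sample size, endpoint and decision rule stay as they are.

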13.1. Specific Statistical Hypothesis Primary Outcome

Among adult hospital admissions with lab-confirmed diagnosis of COVID-19, vadadustat 900 mg will demonstrate superiority to placebo as defined by a lower probability, at treatment day 14, of

death (8) or hospitalization, on invasive mechanical ventilation or ECMO (7) or hospitalization, on non-invasive ventilation or high flow oxygen devices (6) on the NIAID-OS. Generalized linear modeling will evaluate the probability of patients demonstrating this status at day fourteen of treatment as a function of treatment condition after covarying for stratification variables.

Secondary Outcome

Among adult hospital admissions with lab-confirmed diagnosis of COVID-19, vadadustat 900 mg will demonstrate superiority to placebo as defined by a higher probability, at treatment day 14, of recovery on the MSOFA scale (MSOFA = 0). Generalized linear modeling will evaluate the probability of patients demonstrating an MSOFA = 0 at day fourteen of treatment as a function of treatment condition after covarying for stratification variables.

[figure not shown]
